1.2 Study design

IMNM01 is a multicenter, randomized, double-blind, placebo-controlled parallel study to evaluate the safety, tolerability and efficacy of Zilucoplan in IMNM cases who are positive for anti-HMGCR (3-hydroxy-3-methyl-glutaryl-coenzyme A reductase) or anti-SRP (signal recognition particle) autoantibodies.

The planned enrollment is approximately 24 participants.

Participants are randomized at Day 1 to 1:1 ratio in order to receive:

- daily SC doses of 0.3 mg/kg Zilucoplan (12 participants), or
- matching placebo administered SC (12 participants).

Randomization is stratified based on the antibody status (anti-HMGCR+ versus antiSRP+).

Following in-clinic education and training all participants will self-inject daily SC doses of blinded study drug, according to randomized treatment allocation, for the subsequent 8 weeks. Single use pre-filled syringes in injection devices are provided for use during the study.

All standard of care therapy medications for IMNM should be kept at the same doses throughout the study, including corticosteroids, immunosuppressive drugs, and IVIG.

The study is comprised of the Main Portion and the Extension Portion. The Main Portion of the study includes a Screening Period of up to 4 Weeks and an 8 Week Treatment Period.

During the Treatment Period, participants will return to the clinic at Week 1, Week 2, Week 4 and Week 8 for safety, tolerability and efficacy evaluations.

Efficacy assessments include Creatine Kinase (CK) levels, as well as performance outcomes, clinician-reported outcomes and patient-reported outcomes (PRO).

Safety assessments include physical examination, vital signs, electrocardiogram (ECG), clinical laboratory tests, adverse event (AE) monitoring and immunogenicity.

Additional assessments include biomarker testing, pharmacokinetics, pharmacodynamics, and optional pharmacogenomics.

At the end the study Treatment Period, participants have the option to receive Zilucoplan in the Extension Portion of the study provided they meet the Extension Portion selection criteria. Visits during the first 8 Weeks of the Extension Portion are identical to the Main Portion of the study for all participants to ensure appropriate monitoring of participants transitioning from placebo to active treatment.

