4 POPULATIONS FOR ANALYSIS

- **Enrolled Set (ES):** will include in all screened participants including screen failures.
- **Intention-to-Treat Population (ITT):** will include all randomized participants.
- **ITT_{NoCOVID-19}:** will include all ITT participants excluding those with confirmed COVID-19 as observed during any visit of the Main Portion of the study and reported in the AE eCRF form.

Of note, ITT_{NoCOVID-19} will be considered in any analysis specified in the current document during the Main Portion only, provided it differs by at least 15% from the ITT in terms of number of participants.

- **Per Protocol Set (PPS):** will include all participants in the ITT Population who have completed the 8 Week Treatment Period and have no important protocol deviations. Important protocol deviations will be evaluated during ongoing data cleaning meetings prior to unblinding of the data.

If a participant received multiple doses of different study drug (i.e., placebo and 0.3 mg/kg), the patient will be assigned to the dose group which they received at the highest frequency within the Main Portion of the study.

- **Intention to Treat - Extension (ITT_{EXT}):** will include all participants who entered the Extension Portion of the study.
- **Safety Set (SS):** will include all participants who received at least 1 dose of study drug during the Main Portion of the study irrespective if they continued to the Extension Portion. Participants will be analyzed based on the actual treatment received.

If a study participant received multiple doses of different study drug (i.e., placebo and 0.3 mg/kg), the participant will be assigned to the dose group which he/she received at the highest frequency within the Main Portion of the study.

Of note, participants who were on placebo during the Main Portion of the study and continued to the Extension Portion will be included in both groups depending on the study period assessed. Safety results on 0.3 mg/kg across the Main and Extension Portions will be combined.

- **Safety Set No Covid-19 (SSNOCOVID-19):** will include all participants in the SS except those with confirmed COVID-19 (as reported in AE eCRF form) during any time of the study (Main or Extension Portion).
Of note, SSNOCOVID-19 will be considered in any analysis specified in the current document, provided it differs by at least 15% from the ITT in terms of number of participants.

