- Non-Serious TEAEs by PSOC and PT of at least 5% within any IMP (Main Portion) or active treatment (Extension Portion), in SS
- TEAEs by PSOC and PT leading to drug discontinuation, in SS
- TEAEs by PSOC and PT leading to death, in SS

Of note, the following are not considered to be AEs despite requiring hospitalization:

- Pre-existing conditions that, in the opinion of the investigator, did not worsen or progress during study participation
- Routinely scheduled procedures or treatments
- Elective procedures that were scheduled prior to study participation (i.e., signing of the ICF)

Safety tables for the combined Main and Extension Portion of the study, will display the Treatment Emergent Adverse Event Incidence Rate (AEIR) per 100 patient-years of Zilucoplan treatment (thus no placebo arm to be summarized due to limited exposure time as compared to active). Tables will include the PEY per 100 patient years (as defined in Section 5.6.1), number and percentage of participants with a particular TEAE, the exposure adjusted incidence rate (EAIR) followed by 95%CI and the exposure adjusted event rate (EAER):

- EAIR for TEAEs by PSOC and PT, in SS
- EAIR for serious TEAEs by PSOC and PT, in SS

The EAIR is defined as the number of study participants with a specific new TEAE divided by the duration of exposure of all participants (scaled to 100 participant years). The time at risk for a study participant is censored at the date of this event. If a study participant has no events, the total time at risk (i.e. exposure) is used.

Exact Poisson 95% CIs for EAIR are calculated using the relationship between the Poisson and the Chi-square distribution (Ulm, 1990; Fay and Feuer, 1997):

$$\text{Lower Confidence Limit} = x_{2n,\alpha/2}^2/2$$

$$\text{Upper Confidence Limit} = x_{2n(n+1),1-\alpha/2}^2/2$$

where n stands for the number of participants with a specific TEAE for the incidence rate of interest and is the basis for the number of the degrees of freedom for the chi-square quantile for the upper tail probability χ^2 .

The EAER is defined as the total number of TEAEs including repeat occurrences in individual study participants divided by the total time at risk scaled to 100 patient-years. No confidence interval will be computed for the EAER.

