5.6.4.1.2 Individual Subject Changes of Laboratory Values

The laboratory variables that are categorized as normal, high or low based on the reference range as supplied by the analytical laboratory will be presented in shift tables from baseline to each scheduled post-baseline visit by IMP and any post-baseline visit (including unscheduled visits) by IMP.

The number and percentage of participants who meet the criteria with respect to elevated liver function tests and drug-induced liver injuries (PDILI) will be summarized by IMP at each scheduled visit and at any visit (including unscheduled visits), [Table 6-4](#) in Section [6.1.7](#). A listing will also be provided for participants who meet at least one of the criteria.

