^b Corrected Ca (mg/dl) = Ca (mg/dl) + (0.8 [4 - measured albumin (g/dl)]); Corrected Ca = [0.8 x (normal albumin - patient's albumin)] + serum Ca, Karbhari, D.S.; Karbhari, S., Karbhari, N.S.; Patel, S. (2017).

^c Glucose high criterion defined by Grade 3 and higher events according to CTCAE, Version 4.03, June 14, 2010

^d GFR is calculated using the Chronic Kidney Disease Epidemiology Collaboration or CKD-EPI formula (https://qxmd.com/calculate/calculator_251/egfr-using-ckd-epi) which is eGFR = 141 * min(Scr/κ,1)α * max(Scr/κ, 1)-1.209 * 0.993Age * 1.018 [if female] * 1.159 [if black]; where Scr is serum creatinine (mg/dL), κ is 0.7 for females and 0.9 for males, α is -0.329 for females and -0.411 for males, min indicates the minimum of Scr/κ or 1, and max indicates the maximum of Scr/κ or 1. For derivation from values in standard units (umol/L) the κ values are 61.9 for females and 79.6 for males.

The table for the markedly abnormal liver function tests will contain data beyond the CTCAE v5.0 Grade 3 thresholds as outlined in **Table 6-4** above, in order to allow for a more thorough review of elevated liver function tests.

There will be one table by IMP in the SS, which will display the count and percentage of participants meeting the criteria mentioned in **Table 6-4** at any visit during the study (including unscheduled visits). For the combined criteria to be fulfilled the conditions should be present in the same visit.

The liver function results for study participants with markedly abnormal criteria will be listed for all study visits (that is including the not on treatment assessments).

Table 6-4: Markedly Abnormal Criteria for Liver Function Tests

Category	Parameter	Criterion ^a
Drug Hepatic disorders TEAEs	TEAEs in MedDRA SMQ	“Drug related hepatic disorders - comprehensive search (SMQ-narrow scope)” excluding the 2 sub-SMQs of “Liver neoplasms, benign (incl cysts and polyps) (SMQ)” and “Liver neoplasms, malignant and unspecified (SMQ)”
Elevated Liver Function Tests	AST	>3 x ULN, >5 x ULN, >8 x ULN, >10 x ULN, >20 x ULN
	ALT	>3 x ULN, >5 x ULN, >8 x ULN, >10 x ULN, >20 x ULN
	AST or ALT	>3 x ULN, >5 x ULN, >8 x ULN, >10 x ULN, >20 x ULN
	TBL	>1.5 x ULN, >2 x ULN
	ALP	1.5 x ULN
Potential drug-induced liver injury (DILI) criteria	AST or ALT	>3xULN with TBL >1.5xULN
	AST or ALT	>3xULN with TBL >2xULN
	Hy's Law	AST or ALT > 3×ULN with concurrent ALP < 2 × ULN and concurrent TBL > 2×ULN

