^a Meeting the criteria at any post-baseline visit after the first infusion of study medication and within 40-days of the last injection and not meeting the same criteria during baseline

Criteria listed in [Table 6-5](#) will be applied in the determination of PCSA (Potentially Clinically Significant Abnormalities) in vital signs of the study participants.

Table 6-5: Abnormality Criteria in Vital Signs

Parameter	Criterion ^a
Systolic Blood Pressure (mmHg)	≤ 90 mmHg and a decrease from Baseline of ≥20 mmHg ≥ 160 mmHg and an increase from Baseline of ≥20 mmHg
Diastolic Blood Pressure (mmHg)	≤50 mmHg and a decrease from Baseline of ≥15 mmHg ≥105 mmHg and an increase from Baseline of ≥ 15 mmHg
Pulse rate (bpm)	≤50 mmHg and a decrease from Baseline of ≥15 mmHg ≥120 mmHg and an increase from Baseline of ≥15 mmHg

^a Meeting the criteria at any post-baseline visit after the first infusion of study medication and within 40-days of the last injection and not meeting the same criteria during baseline

Criteria listed in [Table 6-6](#) will be applied in the determination of abnormalities in ECG of the study participants.

Table 6-6: Abnormality Criteria in ECG

Parameter	Criterion ^a
QT interval (ms)	≥500ms; ≥60ms increase from Baseline

Parameter	Criterion ^a
QTc(F) (ms)	≥500ms; ≥60ms increase from Baseline
PR interval (ms)	Treatment-emergent value >200ms
QRS interval (ms)	Treatment-emergent value >100ms
Heart Rate (bpm)	<50bpm; >120bpm

^a Meeting the criteria at any post-baseline visit after the first infusion of study medication and within 40-days of the last injection and not meeting the same criteria during baseline

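### The whole-study liver table (SAP 6.1.7) sets a crude zilucoplan percentage pooled over Main and Extension beside 8 weeks of placebo, and no Main-only cumulative count of the Table 6-4 criteria is planned

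*SAP*

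**What the plan says.** SAP 6.1.7, in the text before Table 6-4, plans a single display: "There will be one table by IMP in the SS, which will display the count and percentage of participants meeting the criteria mentioned in" that table. Its time window is "at any visit during the study (including unscheduled visits"). Footnote a of the table limits counted events to those "within 40-days of the last injection and not meeting the same criteria during baseline".

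SAP Section 4, under the Safety Set, fixes the columns. It says that "Safety results on 0.3 mg/kg across the Main and Extension Portions will be combined", and that "participants who were on placebo during the Main Portion of the study and continued to the Extension Portion will be included in both groups", according to the period assessed.

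On follow-up, SAP 1.2 says: "The Main Portion of the study includes a Screening Period of up to 4 Weeks and an 8 Week Treatment Period". Placebo is given in that treatment period only. Protocol Section 7.2 leaves the Extension open-ended, except for an 18-month treatment period in France.

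Elsewhere the SAP treats the same imbalance differently:

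- **Adverse events (5.6.2).** The combined-portion tables carry exposure-adjusted rates for zilucoplan only, "thus no placebo arm to be summarized due to limited exposure time as compared to active".
- **Table 6-3 laboratory criteria, vital signs and ECG abnormalities (5.6.4.1.1, 5.6.4.2.1, 5.6.4.3.1).** These are summarised for the Main and Extension portions.
- **Liver criteria (5.6.4.1.2).** The Table 6-4 criteria are also shown by treatment at each scheduled visit, and again at any visit.

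**The concern.** A participant's chance of ever crossing a threshold cannot fall, and normally rises, as more samples are drawn. A crude percentage over the whole study therefore depends on length of observation as well as on liver risk. The two columns differ greatly in length of observation, and the difference runs one way.

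This is the display meant to screen for liver injury, and it includes the combined DILI and Hy's Law rows. A reader who compares its two percentages would be comparing unequal follow-up, and an excess on zilucoplan in that table alone could not be interpreted. The SAP is also inconsistent with itself. The first row of Table 6-4 is a hepatic adverse-event category. Under 5.6.3 those same events get an exposure-adjusted rate among zilucoplan-treated participants, but in the liver table they get a crude comparison with placebo.

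**Working it through.** The plan states no figure for this table, so there is none to reproduce. The check counts scheduled draws and asks what the table would show if the drug had no effect on the liver.

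**Scheduled post-dose chemistry draws (Protocol Tables 1 and 2)**

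- Placebo: Weeks 1, 2, 4 and 8, so 4. No chemistry is scheduled at the safety follow-up visit.
- Extension to E117: E8, E15, E29, E57 and E117, so 5. Day E1 is the Week 8 visit and is not counted again.
- After E117: one every 3 months, taken as 90 days. To 12 months (about day 365) this adds E207 and E297, so 7 Extension draws. To 18 months (about day 548) it adds E207, E297, E387 and E477, so 9.
- Unscheduled draws and the final Extension visit are left out.

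**Assumptions not in the documents:** the same independent risk p at every draw in both groups, 12 participants per arm, and all 24 entering the Extension.

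**Formula:** P(ever) = 1 − (1 − p)^draws. The zilucoplan column is the mean of the originally randomised participants (4 Main draws plus the Extension draws) and the switchers (Extension draws only).

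| p | Extension | Placebo, 4 draws | Zilucoplan, randomised | Switchers | Pooled | Ratio |
|---|---|---|---|---|---|---|
| 2% | 4 months | 7.8% | 9 draws, 16.6% | 5 draws, 9.6% | 13.1% | 1.7 |
| 2% | 12 months | 7.8% | 11 draws, 19.9% | 7 draws, 13.2% | 16.6% | 2.1 |
| 2% | 18 months | 7.8% | 13 draws, 23.1% | 9 draws, 16.6% | 19.9% | 2.6 |
| 1% | 18 months | 3.9% | 12.2% | 8.6% | 10.4% | 2.7 |
| 5% | 18 months | 18.5% | 48.7% | 37.0% | 42.8% | 2.3 |

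**How far the size depends on the model**

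- *Constant hazard in time.* Assume an 8-week risk of 5% in both groups, so λ = −ln(0.95)/8 = 0.00641 per week. With 18 months (78.3 weeks) of Extension, the pooled percentage is the mean of 1 − exp(−0.00641 × 86.3) = 42.5% and 1 − exp(−0.00641 × 78.3) = 39.5%. That is 41.0% against 5%, a ratio of 8.2. With an 8-week Extension it is 7.4% against 5%, a ratio of 1.5. Exposure at 18 months is 12 × 8/52.18 = 1.84 participant-years on placebo and 12 × (86.3 + 78.3)/52.18 = 37.9 on zilucoplan.
- *Complete correlation within a person.* If the same people cross at every draw and nobody else does, the number of draws does not matter and the ratio is 1.0.

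**Main Portion only.** Both arms have 4 draws, so at p = 2% both show 7.8% and the ratio is 1.0. Under the constant-hazard model both show 5%.

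**The case against.** The strongest reply is that much of what is needed is already planned:

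- SAP 5.6.4.1.2 shows the same liver criteria by treatment at each scheduled visit, so Weeks 1, 2, 4 and 8 can be compared at equal observation time.
- SAP 5.6.4.1.1 with Table 6-3 gives a Main-only overall summary that covers AST, ALT, ALP, gamma-GT and bilirubin.
- Adverse events are reported for the Main Portion separately (5.6.2), and hepatic events of interest get exposure-adjusted rates in the combined data (5.6.3).
- Participants who meet a liver criterion are listed. With about 24 participants, a Hy's Law case can be placed in its portion directly.

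All of this stands. A reader might infer that a true liver excess could not be told apart from longer observation anywhere in the report, and these displays show that this goes too far. They still do not fill the gap. The by-visit display is not cumulative, Table 6-3 uses different thresholds and has no combined criteria, and the summary over any visit in 5.6.4.1.2 has no stated split by portion.

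A reader might also infer that zilucoplan must look worse by construction. The documents do not support that. Table 6-4 counts only criteria not met at baseline, entry requires CK above 1000 U/L, and SAP 6.1.5.7 treats AST and ALT as muscle enzymes. They may fall if treatment works. The bias is upward at equal risk, but the observed direction is not guaranteed.

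Finally, a reader might assume that the laboratory shift tables, given for "any post-baseline visit (including unscheduled visits) by IMP", pool the portions too. SAP 5.6.4.1.2 does not say so, and SAP 5.1.1.4 confines pooling to specific safety analyses. That point is unclear rather than wrong.

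**Conclusion.** The concern holds for the Table 6-4 display over the whole study. It pools zilucoplan across portions, uses crude percentages, and places them beside 8 weeks of placebo. At equal underlying risk the zilucoplan percentage is biased upward. No section provides a Main-only cumulative count of these criteria, including the combined DILI and Hy's Law rows.

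Under independent draws and full Extension entry, the ratio is about 1.7 (4 months, 2% per draw) to 2.3–2.7 (18 months, 5% to 1% per draw). These are illustrations, not predictions. The per-draw risk and the correlation between draws are not in the documents, and the Extension length is given only for France. Correlated draws or incomplete Extension entry would lower the ratio, and the constant-hazard model raises it. The direction at equal risk rests on the design, while the size rests on the assumptions.

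The table is descriptive and does not affect the primary analysis. The change is worth making because the SAP already applies the principle to adverse events.

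**What to change.** In SAP 6.1.7, and for the liver summary over any visit in 5.6.4.1.2, replace the single display with two:

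1. **Main Portion only, by treatment.** Cumulative count and percentage meeting each Table 6-4 criterion, including the combined DILI and Hy's Law rows. State that this is the only zilucoplan-versus-placebo comparison of these criteria.
2. **Main plus Extension, zilucoplan exposure only.** No placebo column, with the exposure-adjusted incidence rate from 5.6.2. Count time at risk to the first visit that meets the criterion.

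Keep the by-visit display and the listings. Add a sentence to 5.6.4.1.2 saying that the laboratory shift tables for any post-baseline visit are also produced by portion.

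The cost is SAP wording and one extra table, with no new data. The Main-only comparison will have small counts, with about 12 participants per arm.

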6.1.8 Compliance

Not Applicable. The number of doses missed will be recorded as detailed in Section 5.6.1.

6.2 Appendix 2: MedDRA Algorithmic Approach to Anaphylaxis

The SMQ *Anaphylactic reaction* consists of three parts:

- A narrow search containing PTs that represent core anaphylactic reaction terms:

Preferred Terms:

- Anaphylactic reaction
- Anaphylactic shock
- Anaphylactic transfusion reaction
- Anaphylactoid reaction
- Anaphylactoid shock
- Circulatory collapse
- Dialysis membrane reaction
- Kounis syndrome
- Shock
- Shock symptom
- Type I hypersensitivity

- A broad search that contains additional terms that are added to those included in the narrow search. These additional terms are signs and symptoms possibly indicative of anaphylactic reaction and categorized in B, C or D:

Category B Preferred Terms:

- Acute respiratory failure
- Asthma

- Bronchial oedema
- Bronchospasm
- Cardio-respiratory distress
- Chest discomfort
- Choking
- Choking Sensation
- Circumoral oedema
- Cough
- Cyanosis
- Dyspnoea
- Hyperventilation
- Irregular Breathing
- Laryngeal dyspnea
- Laryngeal oedema
- Laryngospasm
- Laryngotracheal oedema
- Mouth swelling
- Nasal obstruction
- Oedema mouth
- Oropharyngeal spasm
- Oropharyngeal swelling
- Respiratory arrest
- Respiratory distress
- Respiratory dyskinesia
- Respiratory failure
- Reversible airways obstruction
- Sensation of foreign body
- Sneezing
- Stridor
- Swollen tongue
- Tachypnoea

This document contains neither recommendations nor conclusions of the European Medicines Agency. It is the property of the European Medicines Agency and is made available under the terms of the European Public Database Agreement. It may not be reproduced in whole or in part, nor given to third parties in any format without the prior permission of the European Medicines Agency.

- Throat tightness
- Tongue oedema
- Tracheal obstruction
- Tracheal oedema
- Upper airway obstruction
- Wheezing.

Category C Preferred Terms:

- Allergic oedema
- Angioedema
- Erythema
- Eye oedema
- Eye pruritus
- Eye swelling
- Eyelid oedema
- Face oedema
- Flushing
- Generalised erythema
- Injection site urticaria
- Lip oedema
- Lip swelling
- Nodular rash
- Ocular hyperaemia
- Oedema
- Periorbital oedema
- Pruritus
- Pruritus allergic
- Pruritus generalized
- Rash
- Rash erythematous
- Rash generalized

This document can only be used to support any marketing authorization application and any extensions or variations thereof.
REDACTED COPY

- Rash pruritic
- Skin swelling
- Swelling
- Swelling face
- Urticaria
- Urticaria papular

Category D Preferred Terms:

- Blood Pressure decreased
- Blood Pressure diastolic decreased
- Blood Pressure systolic decreased
- Cardiac arrest
- Cardio-respiratory arrest
- Cardiovascular insufficiency
- Diastolic hypotension
- Hypotension

- An algorithmic approach which combines anaphylactic reaction symptoms in order to increase specificity. A potential anaphylactic reaction is defined as meeting at least one of the following criteria:
 - A narrow term or a term from Category A;
 - A term from Category B - (Upper Airway/Respiratory) AND a term from Category C - (Angioedema/Urticaria/Pruritus/Flush), when both TEAEs occur on two consecutive days, under the condition that Zilucoplan treatment is still ongoing at the first of these two days (both TEAEs will be flagged as anaphylactic reactions)
 - A term from Category D - (Cardiovascular/Hypotension) AND [a term from Category B - (Upper Airway/Respiratory) OR a term from Category C - (Angioedema/Urticaria/Pruritus/Flush)], when both TEAEs occur on two consecutive days, under the condition that Zilucoplan treatment is still ongoing at the first of these two days (both TEAEs will be flagged as anaphylactic reactions)

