- Before the pandemic: a TEAE will be assigned to this period if the start date of the event is on or after the date of the first administration of study drug on Day 1 but before the cut-off date of 11th MAR 2020.
- During/after the pandemic: a TEAE will be assigned to the during/after the pandemic Period if the start date of the event is on or after the date of the first administration of study drug on Day 1 but after the cut-off date of 11th MAR 2020.

A TEAE will be counted as related to study drug if the response to the question “Relationship to Study Medication” is “Related”. Severe TEAEs are those with CTCAE Grade 3 or above, or those without a CTCAE grading classified as ‘severe’ by the Investigator. If a participant reports the same event with different relationship assessments, then participant will be counted under both related and not related categories.

Adverse events will be presented as “number of participants (percentage of participants) [number of events]”. In this style of output, “[number of events]” will include all cases of an AE including repeat occurrences in individual participants, while “number of participants” will count each participant only once.

TEAE Summaries will be reported separately within the Main Portion and within the Main and Extension Portion of the study and presented by primary system organ class (PSOC) and preferred term (PT) within each IMP. PSOCs will be sorted alphabetically. PTs will be sorted by decreasing frequency of Zilucoplan within each PSOC; ties will be sorted alphabetically within Zilucoplan. TEAEs will be mapped to a study portion based on the onset date.

The following summaries will be produced:

- TEAE overview table in SS and SS_{NOCOVID-19}, displaying participants with at least one TEAE, with at least one TEAE before/after 11th March 2020, with at least one serious TEAE, with at least one TEAE resulting to permanent withdrawal from study medication, with at least one drug-related TEAE and with at least one TEAE leading to death
- TEAEs by PSOC and PT, in SS
- TEAEs by PSOC and PT by COVID-19 period, in SS
- Serious TEAEs by PSOC and PT in SS
- Serious TEAEs by PSOC and PT for each COVID-19 period, in SS
- TEAEs by PSOC, PT and maximum CTCAE V5.0 Grade, in SS
- TEAEs by PSOC, PT and maximum relationship, in SS
- Serious TEAEs by PSOC, PT and maximum relationship, in SS
- Fatal TEAEs by PSOC, PT and maximum relationship, in SS

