5.6.3 Adverse Events of Interest

The following bullets define the TEAEs of interest for Zilucoplan:

- **Infections**
 - Serious infections: Serious TEAEs in MedDRA SOC “Infections and infestations”
 - Infections: TEAEs in MedDRA SOC “Infections and infestations”
 - Neisseria infections: TEAEs in MedDRA HLT “Neisseria infections”
 - Serious Neisseria infections: Serious TEAEs in MedDRA HLT “Neisseria infections”
- **Adverse events potentially related to hypersensitivity (including anaphylaxis)**

Potential anaphylactic reactions are defined via a MedDRA algorithmic approach (see Section 6.2), which combines a number of different TEAEs/anaphylactic reaction symptoms. Some cases are dependent on the presence of multiple symptoms/TEAEs (i.e. TEAEs with the same AE onset day or one day later) in order to be classified as an anaphylactic reaction; at least one of the symptoms/TEAEs needs to be serious for the reaction to be classified as a serious anaphylactic reaction.

- Anaphylactic reactions are defined as follows:
 - Serious Anaphylactic reactions: MedDRA algorithmic approach to anaphylaxis where at least one of the TEAEs needs to be serious
 - Anaphylactic reactions: MedDRA algorithmic approach to anaphylaxis among TEAES
- Hypersensitivity reactions are defined as follows:
 - Serious hypersensitivity reactions: Serious TEAEs in MedDRA Standardized MedDRA Query (SMQ) “Hypersensitivity (narrow scope)”

Hypersensitivity reactions: TEAEs in MedDRA SMQ “Hypersensitivity (narrow scope)”

- **Injection site reactions**
 - TEAEs in MedDRA HLT “Injection site reactions” or HLT “Administration site reactions NEC”.
- **Hepatic events and drug-induced liver injuries, Drug related hepatic disorders**
 - TEAEs in MedDRA SMQ narrow scope of “Drug related hepatic disorders - comprehensive search (SMQ)” excluding the 2 sub-SMQs of “Liver neoplasms, benign (incl cysts and polyps) (SMQ)” and “Liver neoplasms, malignant and unspecified (SMQ)”.
- **Malignancies**
 - Malignant or unspecified tumours: TEAEs in MedDRA SMQ “Malignant or unspecified tumours (SMQ)”
 - Malignant tumours: TEAEs in MedDRA SMQ “Malignant tumours (SMQ)”

Note: the events included in the “Malignant tumours” table will be a subset of the events included in the “Malignant or unspecified tumours” table. While the “Malignant tumours (SMQ)” is most relevant, “Malignant or unspecified tumours (SMQ)” will be reviewed for potential malignancies.

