Should an Adverse Event of Interest has not occurred during the study, the corresponding line should be included with zero occurrences.

The following tables will be created:

- TEAEs of interest by PT, in SS,
- EAIR for TEAEs of interest by PT, in SS (combined Main and Extension Portion among participant received at least one dose Zilucoplan).

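### SAP 6.2 ties the symptom-combination criteria for anaphylaxis to ongoing zilucoplan, so combination flags on placebo are zero by construction in the Main Portion

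*SAP*

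**What the plan says.** SAP 5.6.3 names anaphylaxis among the adverse events of interest and takes its definition from the appendix, SAP 6.2. The appendix lists three criteria, any one of which is enough:

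1. "A narrow term or a term from Category A". No treatment or timing condition is attached.
2. A Category B term (airway or respiratory) together with a Category C term (angioedema, urticaria, pruritus, flush).
3. A Category D term (cardiovascular, hypotension) together with a B or a C term.

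Criteria 2 and 3 carry the same two conditions. One is on timing: "when both TEAEs occur on two consecutive days". The other is on treatment: "under the condition that Zilucoplan treatment is still ongoing at the first of these two days".

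SAP 5.6.3 describes the pairing as "TEAEs with the same AE onset day or one day later" and states no treatment condition. It then plans two tables. The first is "TEAEs of interest by PT, in SS". The second, of exposure-adjusted rates, is limited to participants who received zilucoplan.

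Under SAP 4 the Safety Set "will include all participants who received at least 1 dose of study drug during the Main Portion of the study", so it contains the placebo arm. SAP 5.6.2 has adverse event summaries "presented by primary system organ class (PSOC) and preferred term (PT) within each IMP".

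**The concern.** A rule that derives a safety outcome should not depend on the arm. Here the same pair of symptoms, with the same timing, is a potential anaphylactic reaction in a participant on zilucoplan and not in one on placebo. The placebo column is meant to show how often the algorithm fires without the drug. That matters because Categories B and C include non-specific terms such as cough, sneezing, rash and pruritus, which can pair up by chance. With the combination route closed on placebo, that background rate cannot be seen, and nothing in the table would tell a reader that the zero comes from the rule rather than from the data.

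The timing wording is a smaller matter. SAP 6.2 and SAP 5.6.3 describe the same pairing in different words, and two programmers could treat same-day onsets differently.

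**Working it through.** The plan gives no figure to reproduce for this point. The check is to apply the rules as written to each arm, each type of event and each gap between onsets.

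**Inputs.** The three criteria and their conditions come from SAP 6.2, the alternative timing wording from SAP 5.6.3, and the arms from SAP 5.1.1.4, which lists placebo and zilucoplan 0.3 mg/kg as separate groups. The planned 12 participants per arm come from SAP 1.2.

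**Is a Main Portion event flagged?** The result is the same for each of the three pairings (B with C, D with B, D with C). The zilucoplan rows assume that treatment is ongoing.

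| Event | Arm | SAP 6.2, literal timing | SAP 6.2, same day also allowed | SAP 5.6.3 wording |
|---|---|---|---|---|
| Core term (criterion 1) | either | yes | yes | yes |
| Pair, same-day onset | zilucoplan | no | yes | yes |
| Pair, same-day onset | placebo | no | no | yes |
| Pair, onset one day apart | zilucoplan | yes | yes | yes |
| Pair, onset one day apart | placebo | no | no | yes |
| Pair, onset two days apart | either | no | no | no |

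Two things follow. Placebo fails both combination criteria at every gap under either reading of the SAP 6.2 timing rule, so settling the timing does not cure the arm dependence. The timing wordings differ only for same-day pairs, and only if SAP 6.2 is read literally. If the condition referred to study treatment and the SAP 5.6.3 timing applied, both arms would be flagged identically: every pair with a gap of 0 or 1 day, none at 2 days.

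**Which output is affected.** The exposure-adjusted table in SAP 5.6.3 covers only participants who received zilucoplan, and SAP 5.6.2 leaves placebo out of the combined Main and Extension rate tables. Placebo participants who switch in the Extension Portion can meet criteria 2 and 3, but then as zilucoplan events. What remains is the Main Portion summary of adverse events of interest.

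**Possible size.** The documents give no rate for such pairs. Let p be an assumed proportion of participants, equal in both arms, with a pair that meets the timing rule. On zilucoplan the expected number flagged through criteria 2 and 3 is 12 × p, and the chance of at least one is 1 − (1 − p)^12. On placebo both are 0.

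| p (assumed) | Expected on zilucoplan, 12 × p | Chance of at least one | Placebo |
|---|---|---|---|
| 2% | 0.24 | 1 − 0.98^12 = 22% | 0 |
| 5% | 0.6 | 1 − 0.95^12 = 46% | 0 |
| 10% | 1.2 | 1 − 0.90^12 = 72% | 0 |
| 20% | 2.4 | 1 − 0.80^12 = 93% | 0 |

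These are upper figures for each p. If some pairs start on the same day and the literal timing is programmed, those pairs drop out on zilucoplan too, and the count moves towards 0 against 0.

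**The case against.** The best defence is that the wording is merely loose. SAP 5.6.3 applies the algorithm to treatment-emergent events with no arm restriction, and nearby safety text is careless elsewhere: footnotes in SAP 6.1.7 speak of a first infusion in a trial of subcutaneous injections. The table specifications are in a separate document, so the programmed rule cannot be seen. This stands as a caution about what will be programmed. It does not change what is written: SAP 5.1.1.4 keeps the two arms apart by name, SAP 5.6.2 says study drug when it means either arm, and no other section restores placebo eligibility.

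The objection does stand against several stronger inferences that a reader might draw:

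- *That placebo can show no anaphylaxis at all.* Criterion 1 is open to both arms; only the combination flags are closed.
- *That the hypersensitivity comparison is biased too.* SAP 5.6.3 defines hypersensitivity separately, through a narrow standardised query, and injection site reactions through their own terms. Neither carries the zilucoplan condition.
- *That placebo events are lost.* The individual terms still appear in the by-arm tables under SAP 5.6.2 and in the listings. Only the derived flag is missing.
- *That the timing rules are proven to conflict.* The SAP 6.2 phrase does not mention onset and can be read as falling within a two-day span, which agrees with SAP 5.6.3. It is an ambiguity to settle, not a demonstrated loss of cases.
- *That a spurious difference of a particular size, such as 10 percentage points, follows.* Any such figure rests on an assumed pair rate.

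**Conclusion.** The point holds in limited form. As written, the combination criteria in SAP 6.2 cannot be met while a participant is on placebo, so equal true rates of symptom pairs would give unequal flag rates in the Main Portion table. The treatment condition can only raise the zilucoplan count relative to placebo. The conclusion assumes that the text is programmed literally and that the table of events of interest shows both arms, as the Safety Set definition and the general rule for adverse event summaries imply.

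The size is unknown and probably small: about 12 participants per arm, 8 weeks of treatment, one descriptive table and no hypothesis test. Over assumed pair rates of 2% to 20% the imbalance is about 0.2 to 2.4 participants. No primary, secondary or other tested endpoint is involved. It is still worth correcting, because anaphylaxis is a named event of interest, one or two flags against zero would be noticed at this sample size, and the correction costs almost nothing.

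**What to change.** In SAP 6.2, in both combination criteria, replace the reference to zilucoplan treatment with study treatment (zilucoplan or placebo). In the same edit, restate the timing condition in the terms of SAP 5.6.3 (onset on the same day or one day later), so that same-day pairs are not dropped on a literal reading. Check that the separate table specifications carry the same rule, and make the change before the Week 8 data are unblinded.

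The cost is two phrases in the SAP, each appearing in both criteria, and the program for one derivation. Data collection, study conduct and the efficacy analyses do not change. The flag can then also be derived without knowing the allocation.
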